1 K01 AT008219-01A1

## Tool Revision History

Version Number: 2

Version Date: June 11, 2015

Summary of Revisions Made:

- Added the ability to train additional back-up interventionists and have phlebotomists conduct blood draws
- Edited the description regarding timing of data abstracted during chart reviews to be consistent across sections of the protocol
- Changed wording to clarify that the study staff holding randomization would not be the same as those collecting data
- Clarified wording regarding adverse events to state that only AEs related to the study intervention or measures will be captured.

Version Number: 3

Version Date: December 7, 2015

Summary of Revisions Made:

- Modified language for clarification in the description of the active intervention.
- Modified footer in Schedule of Evaluations to match the data safety and monitoring plan regarding identification of adverse events.
- Modified timeframe from one to two weeks in the plan for handling any modifications to the standard schedule.
- Allows for participant preference in the time daily surveys are sent and the ability for a study team member to contact participants to facilitate completion of daily surveys.

---

Version Number: 4

Version Date: March 29, 2016

Summary of Revisions Made:

- Adapted wording to be specific to procedures at new recruitment site, the Comprehensive Cancer Center of Wake Forest University
- Changed personnel to be relevant for the new recruitment site

Version Number: 5

Version Date: December 8, 2016

Summary of Revisions Made:

- Changed Co-Investigator [name] to [name] because of her relocation

Version Number: 6

Version Date: March 1, 2019

Summary of Revisions Made:

- Changed Co-Investigator [name] to [name] because of his relocation
- Changed eligibility criteria and relevant justification

Version Number: 7

Version Date: July 15, 2019

Summary of Revisions Made:

- Updated power analyses to be based upon determining an estimate of the variance.

## PRÉCIS

### Study Title

Programs to Support You During Chemotherapy (Pro-You): A randomized controlled pilot study of yoga compared to an attention control in patients receiving chemotherapy

### Objectives

**Aim 1:** To conduct a pilot randomized controlled trial of a Yoga Skills Training (YST) versus an Attention Control (AC) group among adults with a gastrointestinal (GI) cancer receiving chemotherapy to determine preliminary efficacy for the primary outcome of fatigue, secondary outcome of depressive symptoms, and possible mediators (i.e., psychological stress, circadian disruption, inflammation) as assessed by standard measures.

**Aim 2:** To measure the impact of the YST versus the AC on daily assessments of fatigue, depressive symptoms, and proposed mediators in the same trial and explore relationships among daily and standard assessments.

**Aim 3:** To qualitatively assess perceived efficacy of the YST and AC and acceptability of new methodology through semi-structured interviews in a subset of 20-40 participants.

### Design and Outcomes

We propose a prospective stratified randomized controlled pilot study of the preliminary efficacy of YST as compared to AC on fatigue, depressive symptoms and possible mediators in a sample of people with GI cancer receiving first-line chemotherapy.

Standard recalled assessments of fatigue, depressive symptoms and possible mediators will be collected at four time points (baseline, mid-intervention, post-intervention, 4-week follow-up). Participants will also be asked to complete daily assessments of outcomes, mediators, and adherence to home practice of the intervention via an automated daily survey and wear a wrist actigraphy device for two weeks before and two weeks following the interventions. Inflammatory cytokines will be collected along with patients regularly scheduled blood draws at weeks 2 and 10 and a semi-structured interview conducted after completion of all assessments.

### Interventions and Duration

The YST intervention will be administered individually in the clinic during chemotherapy infusions and patients will be encouraged practice the YST daily at home. Chemotherapy infusions follow a standardized treatment regimen that is given during biweekly visits. [name] developed the YST for a prior study to teach the key

elements of yoga in a manner that would accommodate patients' needs and reduce barriers to adherence during chemotherapy. The YST intervention has been modified for this study to consist of four 30 minute in-person sessions (weeks 2, 4, 6, 8) that instructs skills to enhance mindfulness and promote relaxation.

An empathic attention control group will be employed as the AC to account for the added attention and efficacy expectations of the YST as used in previous studies.

[figure not shown]
In addition, the interventionist will recommend that the patients write brief diary entries daily at home. The number of sessions with a professional, recommended home practice, and home assessments will also be matched to the YST.

The total length of time each participant will be on study is approximately 14 weeks (see Study Schema).

### **Sample Size and Population**

The target population is 44 participants, 22 in each group. Randomization will be stratified by type of cancer (colon, rectal/other better prognosis GI cancers, poorer prognosis cancers) and cancer stage (localized stages II/III or metastatic stage IV) to minimize differences between groups (6 strata total). We will add cancers of the small intestine, anus and appendix to our existing rectal cancer strata since the survival rates are similar. The cancer types with poorer prognoses will be put into the new strata (with <50% 5-year survival rate; cancers of the esophagus, stomach, pancreas, gallbladder, liver).

## Study Schema

## 1. STUDY OBJECTIVES

### 1.1 Primary Objective

- To conduct a pilot randomized controlled trial of the YST versus an AC group among adults with gastrointestinal (GI) cancers receiving chemotherapy to determine preliminary efficacy for the primary outcome of fatigue, secondary outcome of depressive symptoms, and possible mediators (i.e., psychological stress, circadian disruption, inflammation) as assessed by standard measures.

*Hypothesis: The YST will show trends for reducing fatigue and depressive symptoms as assessed with standard recalled measures to a greater degree than the AC and these reductions will be associated with decreases in mediators.*

### 1.2 Secondary Objectives

- To measure the impact of the YST versus the AC on daily assessments of fatigue, depressive symptoms, and proposed mediators in the same trial and explore relationships among daily and standard assessments.
- To qualitatively assess perceived efficacy of the YST and AC and acceptability of new methodology through semi-structured interviews in a subset of 20-40 participants.

[figure not shown]
## 2. BACKGROUND AND RATIONALE

### 2.1 Background on Condition, Disease, or Other Primary Study Focus

**Burden of fatigue and depressive symptoms in gastrointestinal cancers is high.** Gastrointestinal (GI) cancers are among the most prevalent cancers for both men and women, and the number of GI survivors continues to increase. Fatigue, “a subjective state of overwhelming and sustained exhaustion and decreased capacity for physical and mental work that is not relieved by rest,” is reported by a majority (>50%) of patients with GI cancers, co-occurs with other common symptoms such as depression (>30% in patients receiving chemotherapy), and is associated with a decline in post-treatment quality of life. There is overlap in some methods for assessing fatigue and depressive symptoms; however, these symptoms remain moderately correlated even when commonalities are removed. There is also considerable evidence showing that fatigue and depression are distinctly associated with other variables such as quality of life. Further, although chemotherapy is efficacious for increasing survival, it leads to increases in fatigue and depressive symptoms such that symptoms peak approximately 3-5 days following treatment and then improve, however fatigue and depressive symptoms do not return to pretreatment levels in a substantial subset of patients (20-80%). Fatigue and depressive symptoms experienced during treatment are associated with subsequent symptoms. Thus, it is important to address elevations of fatigue and commonly co-occurring depressive symptoms during chemotherapy to improve quality of life in patients with GI cancers.

**Importance of shared biobehavioral mediators of fatigue and depressive symptoms.** The biobehavioral conceptual framework and data suggest that fatigue and depressive symptoms tend to co-occur because they may share underlying mechanisms including psychological stress, circadian disruption (i.e., an altered ratio of nighttime activity to daytime activity) and inflammation. Figure 1 illustrates the potential relationships among these variables using a biobehavioral framework. Data support that psychological stress in cancer patients is associated with fatigue, depressive symptoms, circadian disruption and inflammation. Cancer and its treatment can also lead to circadian disruption, which is associated with fatigue in GI cancer patients, and fatigue and depressive symptoms during chemotherapy. Further, evidence suggests that circadian disruption precedes fatigue and depressive symptoms. Data also show that increases in inflammation (i.e., sTNF-R1, IL-6) specifically

during treatment for gastrointestinal cancer is related to changes in fatigue and other symptoms (e.g., distress).

## 2.2 Study Rationale

**Preliminary efficacy of yoga for fatigue and depressive symptoms.** Despite the high symptom burden, there are few behavioral interventions designed for GI cancer patients that aim to proactively improve fatigue and depressive symptoms during treatment. Guidelines for managing cancer-related fatigue include non-pharmacologic and pharmacologic interventions that target fatigue itself, comorbid medical conditions and coexisting symptoms (e.g., depressive symptoms). Both psychological and exercise interventions show efficacy for reducing fatigue and depressive symptoms and reviews suggest that a combined approach may be optimal. However, most existing interventions for GI cancer patients do not use a combined approach. One intervention designed for a heterogeneous group of cancers did apply a combined approach during chemotherapy, yet only found efficacy for depressive symptoms and not fatigue. Yoga utilizes a combined approach and has shown efficacy for reducing fatigue and depressive symptoms when implemented as group classes primarily in patients with breast cancer though has not been investigated when implemented during chemotherapy except for in my Preliminary Research. The key practices taught by yoga are meditation, body movements, and breathing techniques. Therapeutic applications of yoga can target the instructed practices specifically to a goal, such as fatigue, which may improve upon effects found from more general strategies used thus far. This notion is supported by a systematic review that revealed that behavioral interventions targeted to specifically address fatigue have increased efficacy. Although the optimal dose of yoga is

unknown, the greatest improvements in fatigue were found in cancer survivors who practiced yoga an average of three times per week and a review of exercise interventions (including yoga) during chemotherapy found that 90-120 minutes of moderate activity per week was better than higher doses. Further, ~20 minutes of home yoga practice per day was associated with an improvement in next day fatigue. Therefore, a reasonable suggested dose for yoga during chemotherapy would be 3-6 times per week for about 20 minutes per session. In summary, yoga is a promising intervention that incorporates a combined and targeted approach for reducing fatigue and depressive symptoms during chemotherapy that has yet to be investigated in patients with GI cancers.

**Proposed mediators of the effect of yoga on fatigue and depressive symptoms.** Reviews of yoga research call for the investigation of mediators to explain how yoga influences cancer-related outcomes such as fatigue and depressive symptoms. The Self-regulation Framework can be applied to understand the efficacy of behavioral integrative medicine interventions such as yoga. This framework posits that people are able to consciously alter their cognitive (e.g., mindfulness), emotional (e.g., feelings of relaxation) and behavioral (e.g., breathing) responses to various experiences (e.g., psychological stress from cancer and its treatment) to obtain desired goals (e.g., reduced fatigue). Conscious attention to and awareness of the present moment, or mindfulness, is proposed to be the first step in the self-regulation process. Yoga aims to increase mindfulness and promote relaxation to strengthen patients' ability to regulate their responses. There is evidence supporting that yoga reduces psychological stress, and improves subjective and objective sleep quality (a component of circadian disruption). Further, inflammatory cytokines are theoretical biomarkers of effective self-regulation and there is some evidence that yoga reduces inflammation (e.g., IL-6, TNF- $\alpha$ ). Therefore, further study of yoga for reducing fatigue is warranted.

**The proposed yoga intervention, Yoga Skills Training (YST), will be implemented in the clinical setting to be inclusive of patients most in need of intervention.** Implementation of the proposed YST individually in the clinical setting challenges the current paradigm in the United States that typically implements yoga as group classes. A study that recruited cancer patients to group yoga classes found that there were some common barriers to participating in yoga classes including, transportation, scheduling, being too busy or too sick. This was important to consider in this study design because such a large portion of cancer patients travel long distances for treatment (i.e., 83% of colorectal cancer patients treated at Vanderbilt-Ingram Cancer Center travel more than 10 miles for treatment and 48% travel 50 miles or more). Patients' experience of fatigue was also associated with attending fewer yoga classes in another study. Therefore, patients who are burdened by fatigue or depressive symptoms during chemotherapy may be unintentionally excluded from yoga interventions due to feasibility issues. The proposed 30-minute YST can be taught to 2-3 participants in the time generally allocated to one yoga class. Therefore, the number of participants who attend each class is important to consider. In summary, the proposed YST is designed to lessen identified barriers to

participation by integrating YST into patients' already scheduled visits for chemotherapy. So far, only preliminary research has been conducted to explore if yoga can be safe and efficacious when applied in clinical settings related to cancer care. Yet, therapeutic yoga is traditionally implemented individually. Data supporting the efficacy of the YST would encourage a shift in the practice of implementing yoga primarily as a complementary modality to integrating yoga during clinical cancer care to broaden the population of patients who may benefit.

**Daily measurement of fatigue and depressive symptoms will more accurately detect efficacy than more commonly used recalled assessments.** Fatigue and depressive symptoms are generally assessed in intervention studies through retrospective patient-reported outcomes (e.g., "how much fatigue have you experienced in the past 7 days"). However, assessment over a week's time period is likely to miss the acute variation in the experience of symptoms and not capture the influence of an intervention on fatigue at its worst 3-5 days after chemotherapy infusions. That is, daily symptom assessment can improve upon recalled assessments by elucidating the immediate effect of an intervention on the trajectory of symptoms following chemotherapy. Daily diaries are one method for measuring an experience in a participant's natural setting with low patient burden. Fatigue and depressive symptoms will be assessed daily to reduce recall bias and enable detailed analyses of how experiences interrelate on a daily basis. Few studies have utilized daily measures of chemotherapy-related symptoms and this study will be the first to evaluate the impact of an intervention on daily fatigue and depressive symptoms during chemotherapy for GI cancers.

**Assessing the impact of yoga on biobehavioral mediators during chemotherapy is also novel.** The impact of yoga on psychological stress, circadian disruption, and inflammation during chemotherapy has not been investigated. Two pilot studies by the same research team have utilized daily assessment to evaluate the impact of yoga on "positive" therapeutic processes (i.e., invigoration, acceptance, relaxation), however, psychological stress, circadian disruption and inflammation were not assessed. There is some support for the association between yoga and psychological stress, objectively measured rest, and inflammation, but these relationships have not been explored daily during chemotherapy.

**Preliminary Intervention Effects of the YST.** [name] developed an initial protocol for implementing the YST with patients undergoing chemotherapy for ovarian cancer. Data from seven women who participated in the YST during chemotherapy showed an immediate effect. Women completed two Visual Analogue Scale items of anxiety and relaxation immediately before and after the YST. Anxiety decreased and relaxation increased after the YST. Effect sizes were large (anxiety,  $d=-0.82$ ; relaxation,  $d=0.83$ ). Hospital staff did not find the YST burdensome and it was feasible to conduct the YST in a clinical setting. In addition, this study supported the safety of implementing the YST during chemotherapy. Minimal risk including potential for muscle soreness from the gentle movements or emotional discomfort from breathing and meditation practices is expected from participating in the YST.

**Preliminary Feasibility of the YST for GI Cancers.** [name] also conducted a randomized pilot trial of the YST as compared to an attention control group for patients receiving chemotherapy for colorectal cancer. Of the 29 patients approached, 15 (51.7%) agreed to participate with interest from both men (60%) and women (40%). Most (80%) of the in-person intervention sessions (YST or active control) were completed with missed sessions due to patients not receiving chemotherapy. The active control consisted of empathic attention. Thus, these preliminary data support feasibility for recruitment and randomization. Based on what the PI learned from this initial pilot, and with input from my current mentors and other experts, we plan to build upon this previous YST by implementing more robust and innovative measurement (i.e., daily assessments of symptoms, objective measure of circadian disruption, mixed-methods follow-up assessment) and enhancing the YST intervention (i.e., more targeted to fatigue, attention to treatment fidelity, focused on adherence to home practice).

### 3. STUDY DESIGN

We propose a prospective stratified randomized controlled pilot study in a sample of GI cancer patients receiving first-line Fluorouracil (5FU)-based chemotherapy (5FU-based chemotherapy is the standard treatment for all patients with colorectal cancers and most patients with other gastrointestinal cancers). This study will assess preliminary efficacy of YST on the primary outcome of fatigue, secondary outcome of depressive symptoms, and possible mediators (i.e., psychological stress, circadian disruption, inflammation) as assessed by standard measures. Secondary objectives are to measure the impact of the YST versus the AC on daily assessments of fatigue, depressive symptoms, explore relationships among daily and standard assessments, and explore mediators. At study completion, the first 20-40 participants will be selected for semi-structured interviews to discuss perceived impact of the intervention, and adherence to home practice, and acceptability of measures. Overall, the study is designed to help inform a larger future study.

Standard recalled assessments of fatigue, depressive symptoms and possible mediators will be collected at four time points (baseline, mid-intervention, post-intervention, 4-week follow-up). Participants will also be asked to complete daily assessments of outcomes, mediators, and adherence to home practice of the intervention via an automated daily survey and wear a wrist actigraphy device for two weeks before and two weeks following the interventions. Inflammatory cytokines will be collected along with patients regularly scheduled blood draws at weeks 2 and 10 and a semi-structured interview conducted after completion of all assessments.

The YST intervention will be administered individually in the clinic during chemotherapy infusions and patients will be encouraged practice the YST daily at home. Chemotherapy infusions follow a standardized treatment regimen that is given during biweekly visits. [name] developed the YST for a prior study to teach the key elements of yoga in a manner that would accommodate patients' needs and reduce barriers to adherence during chemotherapy. The YST intervention has been modified for this study to consist of four 30 minute in-person sessions (weeks 2, 4, 6, 8) that

instructs skills to enhance mindfulness and promote relaxation.

An empathic attention control group will be employed as the AC to account for the added attention and efficacy expectations of the YST as used in previous studies. In addition, the interventionist will recommend that the patients write brief diary entries daily at home. The number of sessions with a professional, recommended home practice, and home assessments will also be matched to the YST.

The total length of time each participant will be on study is approximately 14 weeks. The enrollment period for the trial is expected to continue for 30 months.

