Based on prior longitudinal work with patients from similar populations, we are anticipating approximately 15% dropout (from N=44). From previous research in a mixed sample of cancer patients, the variability in the values of the PROMIS 7-item fatigue measure used in this study is a standardized standard deviation of 8 points (Mean t-score=53.6). Effect sizes in preliminary studies of yoga for fatigue as compared to an active control in patients with cancer range from 0.33 to 1.50. This variability may be explained in part by study quality and patients' initial levels of fatigue. We expect that daily assessments of fatigue and depressive symptoms will detect these symptoms at their nadir and thus may be more sensitive to such phenomena than recalled measures. Therefore, it is important to obtain a good estimate of the variance of fatigue in this group to use in future studies. Power calculations for a subsequent larger study will be based on clinically meaningful differences between the groups on the primary outcome using estimates of SD. With a sample size of 44, the probability is 0.80 (80% confidence) that the estimate of the standard deviation (SD) will be no more than 10% of the true population SD below the true population SD; if the SD varies by group, there is 80% confidence that the estimate of the SD is no more than 14% below the true SD.

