**Specific Aim 2.** A critical element of this proposal is the inclusion of daily (vs. standard recalled) assessments of fatigue, depressive symptoms and proposed mediators, during two 2-week periods in the study (initial: 0-2 weeks, later: 8-10 weeks). Summaries of the proportion and frequency of missing daily assessments will inform the feasibility of collecting this type of data. Graphical displays of these daily reports will prove invaluable for informing both the patterns of the respective symptoms and mechanisms in and of themselves, and also for informing the optimal representation of the patterns in analyses with the recalled measures. Depending on missing data, study group differences in daily (or mean 2-day) values will be evaluated using mixed-effects generalized linear modeling. Findings and effect sizes garnered from these analyses will be compared to those resulting from recalled measures. Informed by the graphical displays, several summary indices of each of the two daily assessment periods (peak value, mean, coefficient of variation) will be generated for use in multi-method, multi-trait analyses of similarities and differences in the patterns of associations among the daily and recalled measures. This analysis will further inform which measures (and/or which summary indices) appear to be the best and most sensitive indices to use in future studies.

**Specific Aim 3:** Open-ended and interview data will be coded by the Qualitative Research Core led by [name] (Collaborator). [name] will consult with the Core to develop a coding system and also code 10% of the responses to assess reliability. Coded responses will be interpreted with a thematic analysis. The number of participants interviewed (20-40) will be decided by when thematic saturation is reached. Qualitative information gained will enrich quantitative results and inform the protocol of a larger trial.

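### Interviewing the first 20-40 participants can miss the cancer types added during the trial if interviewing stops near 20

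*Combined protocol and SAP*

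**What the plan says.** **Who is interviewed.** Section 3 states: "At study completion, the first 20-40 participants will be selected for semi-structured interviews". Aim 3 in the Précis covers perceived efficacy of both programmes and "acceptability of new methodology through semi-structured interviews in a subset of 20-40 participants". No section selects interviewees by arm, cancer type, stage or site.

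**When interviewing stops.** Section 9.6, Specific Aim 3: "The number of participants interviewed (20-40) will be decided by when thematic saturation is reached". The text does not say whether saturation is judged overall, by arm or by stratum.

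**Who is in the trial.** Précis, Sample Size and Population: "The target population is 44 participants, 22 in each group". The same paragraph says "We will add cancers of the small intestine, anus and appendix to our existing rectal cancer strata", and, for esophagus, stomach, pancreas, gallbladder and liver, "The cancer types with poorer prognoses will be put into the new strata". The Tool Revision History records an eligibility change at Version 6, dated March 1, 2019: "Changed eligibility criteria and relevant justification". Section 9.2 sets no sample size goal within strata and expects about 15% dropout.

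**When and how the interview is held.** Sections 6.2 and 6.2.5 place it after all other data collection, at the Week 14 visit, in person or by telephone.

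**The concern.** Selection by order of entry does little harm when early and late entrants are alike. Here they are not. The Précis contrasts existing strata with new ones, so the earliest participants come from a narrower set of cancers. The saturation rule adds to this: themes from a more uniform early group may start to repeat, and interviewing may close, before anyone with an added cancer type is reached.

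Sections 9.1 and 9.6 say that the qualitative findings are meant to inform a larger trial. If that trial keeps the wider eligibility, its designers could be without interview evidence on acceptability and barriers from the added types, including the whole poorer-prognosis stratum.

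**Working it through.** The range of 20 to 40 has no derivation in the plan, so there is no figure to reproduce. The check asks how many later entrants the stated rule reaches.

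**Inputs**
- N = 44 participants (Précis).
- K = 20 to 40 interviews (Sections 3 and 9.6).
- Dropout 15% (Section 9.2): 0.15 × 44 = 6.6, leaving 37.4, about 37.
- M = number who entered before the widening. The documents do not give it; 10, 20 and 30 are shown as assumptions.

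**All participants can be interviewed.** Later entrants interviewed under the stated rule = max(0, K − M), out of N − M. In-proportion selection from all 44 would give K × (N − M)/N on average.

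| M (assumed) | Later entrants | K = 20: rule / in proportion | K = 30 | K = 40 |
|---|---|---|---|---|
| 10 | 34 | 10 / 15.5 | 20 / 23.2 | 30 / 30.9 |
| 20 | 24 | 0 / 10.9 | 10 / 16.4 | 20 / 21.8 |
| 30 | 14 | 0 / 6.4 | 0 / 9.5 | 10 / 12.7 |

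The last 24, 14 and 4 entrants go uninterviewed at K = 20, 30 and 40. Later entrants may also have colon or rectal cancer, so each count is a ceiling on interviewees with an added type.

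**Only completers are interviewed**, with 15% dropout spread evenly over order of entry. Reaching K interviewees takes K/0.85 entrants.
- K = 20: 20/0.85 = 23.5, so with M of about 24 or more no later entrant is reached.
- M = 10: 0.85 × 10 = 8.5 early interviewees, leaving 11.5 of 20 from later entrants.
- M = 20: 0.85 × 20 = 17 early interviewees, leaving 3 of 20.
- M = 30: 0.85 × 30 = 25.5, which exceeds 20, leaving none.
- K = 40: 40/0.85 = 47.1, which exceeds 44. Every completer is interviewed and the gap is gone.

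The result depends on M and on where in the 20-40 range interviewing stops. The plan fixes neither.

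**The case against.** The strongest reply is that the gap arises only towards the lower end of the range. At 40 interviews at most 4 of 44 are missed, and none if about 37 complete. The protocol also gathers related evidence outside the interviews. Section 6.2 asks for reasons for declining and for dropping out, Section 9.6 analyses drop-out and missing assessments and summarises missing daily surveys as feasibility data, and Sections 5.4 and 6.2 track attendance, home practice and completion of assessments. All of this stands and limits what is at stake. It does not remove the point, because the plan allows a stop at 20 and process data do not replace an interview on experience and barriers.

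A reader might infer more than the documents support:

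- **That participants with low home practice are left out.** Order of entry does not select on practice. A low-practice participant who finishes the assessments is as likely to be interviewed as any other.
- **That saturation is pooled over arms.** Section 9.6 is silent, and Aim 3 names both arms.
- **That some 7 of 44 can never be interviewed.** The 6.6 is anticipated dropout, not an interview exclusion. Section 6.2.5 ends monitoring for patients terminated from the study, but it also provides for remote follow-up of those who change treatment location, and telephone interviews are allowed.
- **That acceptability is overstated.** It may be. The documents do not show that the added cancer types find the programme or the measures more burdensome, and Section 4.1 requires performance status of 1 or better of everyone.

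**Conclusion.** The point holds as a possibility that the stated rule permits. With interviewing stopped at 20, no participant with an added cancer type is interviewed if 20 or more entered before the widening, or about 24 or more if only completers are interviewed. With 10 early entrants, 10 of 20 interviewees (about 11.5 among completers) would be later entrants, against 15.5 under in-proportion selection. Near 40 interviews little or nothing is lost.

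This rests on three assumptions. M is unknown. The widening is read from the Précis wording; the Version 6 log entry records that eligibility changed but not how. The larger trial's population is not defined, so its keeping the wider eligibility is a reasonable inference only. The original cancer types would be represented in any case; the loss concerns the added ones. No quantitative outcome is affected, so this is a low-cost improvement and not an error in the plan.

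**What to change.** In Section 3, replace selection by order of entry with selection of 20 to 40 participants that covers both arms and each of the three cancer-type strata, as far as participants are available. In Section 9.6, state that saturation will not be declared until participants from both arms and from the added cancer types have been interviewed, and that interviewee counts by arm and stratum will be reported. Where they consent, participants who stopped the intervention early may be invited by telephone, a mode already allowed; Section 6.2.5 should then say so. If early interviews are already done, the remaining places can go to the groups not yet covered.

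The cost is a change of wording and a longer interviewing period. At the 18 patients a year expected in Section 9.4 (1.5 a month), the 20th participant enters at about month 13 (20/1.5 = 13.3) and the 44th at about month 29 (44/1.5 = 29.3), so interviewing may run to the end of accrual. More than the minimum of 20 interviews may be needed, still within the limit of 40. Two arms by three cancer types make six cells with no recruitment goal in any of them. Some may hold few or no participants, which is why coverage is asked for only as far as available.
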